8.3.2. Discontinuation of Study Treatment

Subjects will be discontinued from the study treatment in the following circumstances:

- If Exclusion Criteria [9] (with the exception of the hepatic laboratory values; Section 10.4.4), [11] to [15], [18] to [21], [23] and [24] are observed or develop after study enrollment, the subject will be discontinued from the study treatment at the next visit or sooner.
- If in the investigators judgment, the subject is not at least 80% compliant with study treatment (i.e.; investigator recommended dose adjustments based on algorithms)
- If the subject is off study medication for more than 7 consecutive days during the study treatment period.

In the event that the subject is discontinued from the study treatment, the investigator should encourage the subject to remain in the study for continued safety monitoring.

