8.3.3. Subject Discontinuation from the Study

If exclusion criterion [25] through [28] is observed or develops after entry or enrollment, the subject will be discontinued from the study at the next site visit or sooner in the event of a safety exclusion criterion.

Subjects who discontinue the study early will have ET procedures performed as shown in the Study Schedule ([Attachment 1](#)). For information as to how efficacy and safety analyses will be conducted for subjects who are discontinued from study treatment, see Sections 12.2.3 and 12.2.10, respectively.

The subject may be discontinued from the study if:

- Enrollment in any other clinical trial involving an investigational product or enrollment in any other type of medical research judged not to be scientifically or medically compatible with this study.
- Investigator decision
 - The investigator decides that the subject should be discontinued from the study (this can be for safety reasons, such as for recurrent hypoglycemia, or it can be for any reason).
 - If the subject, for any reason, requires treatment with another therapeutic agent that has been demonstrated to be effective for treatment of the study indication, discontinuation from the study occurs prior to introduction of the new agent.
- Subject decision
 - The subject requests to be withdrawn from the study.

- Sponsor decision
 - Lilly or its designee stops the study or stops the subject's participation in the study for medical, safety, regulatory, or other reasons consistent with applicable laws, regulations, and good clinical practice (GCP).
- Adverse event
 - If the investigator decides that the subject should be withdrawn because of a SAE, treatment emergent adverse event (TEAE), or a clinically significant laboratory value, study treatment is to be discontinued and appropriate measures are to be taken. Lilly or its designee is to be alerted immediately. Refer to Safety Evaluations Section [10.4](#).

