9.9.2. Continued Access to Study Treatment

The U-500R insulin used in this study is commercially available in the US and is therefore available for subjects after the conclusion of this study.

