9.11. Concomitant Therapy

All concomitant therapies that are part of routine care are allowed and may be used during the study with the exception of those specifically outlined in Sections 8.1 and 8.2. Subjects who take any excluded concomitant therapy will be discontinued from the study treatment at the next visit or sooner. In emergency/urgent situations, subjects may cease taking study medication for 7 consecutive days and may be treated instead with nonstudy insulin during that time. If a subject takes nonstudy insulin for more than 7 consecutive days, then discontinuation criteria apply (Section 8.3.2).

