OmniPod U-500 Exit Questionnaire for CSII subjects																		X	X ^h
Study Drug/Devices/Diaries																			
Dispense and training of glucose meter	X																		
Education on diabetes lifestyle and diet		X		X															
Training on OmniPod U-500 (CSII treatment arm only)					X ⁱ	X ⁱ													
Dispense study diary	X	X		X	X	X	X			X			X		X				
Collect study diary		X		X	X	X	X			X			X		X		X	X	
Dispense study drug				X	X ^k	X ^k	X ^k			X ^k			X ^k		X ^k				
Collect study drug					X	X	X			X			X		X		X	X	
Dispense subject supplies	X	X		X	X	X	X			X			X		X				
Dispense OmniPod U-500 supplies (CSII treatment arm only)						X	X			X			X		X				

Study Schedule, Protocol B5K-MC-IBHD

Visit 6: CSII Treatment Arm Begins

	S	Lead- In		R	Transition			Treatment Period										ET ^a
Visit Number	1	2	3	4	5	6	7	8	9	10	11	12	13	14	15	16	17	
Week of Study (week prior to visit)	-3	-2	-1	0	1	2	3	4	6	8	10	12	14	17	20	23	26	
Allowable Range (± d=days, w=weeks)	-	1w	3d	1w	3d	3d	3d	3d	3d	3d	3d	3d	3d	3d	3d	3d	1w	
Telephone (T) or Office (O) Visit	O	O	T	O	O	O	O	T	T	O	T	T	O	T	O	T	O	
Study Drug/Devices/Diaries, Cont																		
Dispense nutrition bars		X		X	X	X	X			X			X		X			
Adjust/record insulin dose		X	X	X	X	X	X	X	X	X	X	X	X	X	X	X	X	X
Product complaints					X	X	X	X	X	X	X	X	X	X	X	X	X	X

Abbreviations: AE = adverse event; BG = blood glucose; CRF = case report form; d = day; ET = early termination; HbA1c = Hemoglobin A1c; IWRS = interactive web response system; O = office, R = randomization, S = screening; SAE = serious adverse event; SMBG = self-monitored blood glucose; T = telephone; TRIM-D = treatment-related impact measure for diabetes; TRIM-DD = treatment-related impact measure for diabetes device; w = week.

- a Early termination visit only performed on subjects who did not complete the full 26 weeks of the study.
- b Prior to randomization at Visit 4, all subjects will be re-confirmed for inclusion criteria [1], [2], and [7] and exclusion criteria [18].
- c Central laboratory unless otherwise specified. Laboratory tests may be performed at any time at the investigator’s discretion in the event of an adverse event.
- d Serum screening pregnancy test will be performed at Visit 1 for women of childbearing potential by a Lilly-designated central laboratory. A urine pregnancy test may be repeated locally for any follow-up visits.

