## 5.9. Primary Outcome and Methodology

The primary efficacy measure is change from baseline to the 26-week HbA1c value. The primary analysis will be conducted for the ARS population in Group A. There will be 2 primary analysis methods for different purposes as follows.

1. Per FDA's request, the analysis method will use the copy reference approach to impute missing data based on multiple imputations with a pattern mixture model (later referred to as 'copy reference multiple imputation analysis'). This analysis will include post study treatment discontinuation data. The reference is all observed data from all randomized subjects in the U-500R MDI arm who discontinued study treatment but completed the study without missing data. After imputation, an ANCOVA with baseline HbA1c as a covariate, treatment (U-500R CSII, U-500R MDI) and the stratification factor (U-500R at entry versus other insulins) as fixed effects will be used to analyze the 26-week HbA1c including imputed values.

If in the reference group mentioned above there is only a limited number of subjects and this leads to a failure in performing the proposed multiple imputation analysis, the reference will be changed to include all observed data from all randomized subjects in the U-500R MDI arm who do not have missing data.

2. For manuscripts and other non-FDA submission purposes, an MMRM model that does not include post study treatment discontinuation data and adjusts for missing data through an observed-data-likelihood-based approach will be used. The model will include the following fixed effects: treatment (U-500R CSII, U-500R MDI), weeks on treatment, the interaction between treatment and weeks, and the stratification factor (U-500R at entry versus other insulins). The model will also include baseline HbA1c as a covariate.

As a sensitivity analysis to the missing at random assumption of MMRM model, a stress test will be performed. The missing data are first imputed with the missing at random assumption. Prior to multiple-imputation analysis, in the CSII arm the imputed values will be replaced by the imputed value plus delta. Multiple values of delta within a clinically reasonable and meaningful range will be tested (delta=0.1, 0.2, 0.3, 0.4) to assess if the conclusion from the MMRM primary analysis changes.

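### Protocol 8.3.3 allows a subject who needs another effective agent to be taken out of the study, which can cost the FDA analysis an off-treatment Week 26 HbA1c

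*Protocol*

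**What the plan says.** Protocol 8.3.3 opens its list with "The subject may be discontinued from the study if". Two bullets stand under investigator decision. The first allows withdrawal for safety or for any other reason. The second covers a subject who needs another agent known to work for the study indication, and there "discontinuation from the study occurs prior to introduction of the new agent".

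Protocol 8.3.2 lists reasons to stop study treatment. They include exclusion criterion [18] (glucose-lowering drugs outside the permitted list) arising after enrollment, and more than 7 consecutive days off study medication. In these cases "the investigator should encourage the subject to remain in the study for continued safety monitoring".

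Protocol 9.11 says: "Subjects who take any excluded concomitant therapy will be discontinued from the study treatment at the next visit or sooner". It tolerates up to 7 days of nonstudy insulin in urgent situations. Past that point, "If a subject takes nonstudy insulin for more than 7 consecutive days, then discontinuation criteria apply", and the section cited is 8.3.2, not 8.3.3.

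Protocol Section 11 presents retention after stopping treatment as a way to reduce missing data. SAP 5.4 plans to count subjects who stopped treatment but completed the study.

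Of the FDA-requested primary analysis, SAP 5.9 says: "This analysis will include post study treatment discontinuation data". Its imputation reference is MDI subjects who stopped treatment yet completed the study with no missing data. If that group is too small, the reference becomes all MDI subjects without missing data. The other primary analysis, an MMRM, leaves out data collected after treatment was stopped.

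Attachment 1 schedules HbA1c and FPG at Visit 17 with no condition on current treatment, and also at early termination: "Early termination visit only performed on subjects who did not complete the full 26 weeks of the study".

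**The concern.** The FDA analysis depends on HbA1c values at Week 26 from subjects who are no longer on study treatment. A subject who needs a different glucose-lowering agent is a natural source of such a value. Examples are a Group A subject who needs a GLP-1 receptor agonist or SGLT2 inhibitor, which Table IBHD.9.7 allows in Group B only, or a subject who goes back to a U-100 insulin. The 8.3.3 bullet describes ending follow-up of that subject before the new agent starts. What remains is an HbA1c at exit and an imputed Week 26 value.

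The same event can also be handled in two ways. A site that asks before prescribing may apply 8.3.3 and withdraw the subject. A site that reports the drug afterwards would apply 8.3.2 or 9.11 and keep the subject. Need for another agent may reflect poor glycemic response, so the lost values need not resemble the others. The trial is open-label, so use of the bullet could differ by arm.

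**Working it through.** **The plan's own figure.** Inputs from SAP 5.1: margin 0.4, SD 1.1, two-sided alpha 0.05, power 80%, 25% dropout, 1:1 allocation. A true difference of 0 is assumed because none is stated.

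- n per arm = 2 × (1.960 + 0.842)² × 1.1² / 0.4² = 118.7, rounded up to 119, or 238 in total. The plan says 240.
- Power at 120 per arm is 80.4%. The plan says 80%.
- 240 / (1 − 0.25) = 320 randomized, as planned.

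The sample size reproduces and is not in question here.

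**The texts side by side.**

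| Event | 8.3.3 bullet | 8.3.2 / 9.11 |
|---|---|---|
| Another effective agent is needed, not yet started | Study exit first (permissive list) | Not addressed directly |
| Excluded glucose-lowering drug already taken | Not addressed directly | Stop study treatment; 8.3.2 encourages staying |
| Nonstudy insulin for more than 7 days | Could be read as covering it | Sent to 8.3.2: stop study treatment |

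The overlap is partial, and neither document ranks the sections. For efficacy handling, 8.3.3 refers the reader to 12.2.3, which is the disposition section and does not settle the matter.

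**Effect of one lost value.** Group A has 320 / 2 = 160 per arm. If the imputed value is off by d points, the arm mean moves by d / 160.

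- d = 0.5 (assumed): 0.5 / 160 = 0.0031 points, or 0.8% of the 0.4 margin.
- d = 1.0 (assumed): 1.0 / 160 = 0.0063 points, or 1.6% of the margin.

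**Several lost values, illustration only.** Noncompleters per arm: 160 × 0.25 = 40, assumed equal in both arms. Let r be the share who would attend Week 26 if the bullet were not applied, and s the share of those whom it removes. Both are assumed. Values lost per arm are k = 40rs. The MDI reference is at most 40r(1 − s). This is an upper bound, because a reference subject must have no missing data and not merely a Week 26 value.

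| r | s | k per arm | MDI reference, at most | Arm shift, d = 0.5 to 1.0 |
|---|---|---|---|---|
| 0.25 | 0 | 0 | 10 | 0 |
| 0.25 | 0.1 | 1 | 9 | 0.003 to 0.006 |
| 0.25 | 0.2 | 2 | 8 | 0.006 to 0.013 |
| 0.25 | 0.5 | 5 | 5 | 0.016 to 0.031 |
| 0.50 | 0 | 0 | 20 | 0 |
| 0.50 | 0.1 | 2 | 18 | 0.006 to 0.013 |
| 0.50 | 0.2 | 4 | 16 | 0.013 to 0.025 |
| 0.50 | 0.5 | 10 | 10 | 0.031 to 0.063 |

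The last row's upper end is 10 × 1.0 / 160 = 0.0625 points, or 15.6% of the margin. It requires half of all noncompleters to be willing to attend, half of those to be removed by this one bullet, and a full-point error in the same direction for each. Losses in both arms would partly cancel in the treatment difference.

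**The case against.** The strongest reply is that the specific and mandatory texts already give the right answer. Section 8.3.2 says what will happen, while 8.3.3 only says what may. For excluded drugs and prolonged nonstudy insulin, 9.11 names the consequence and it is not study exit. Section 11 and SAP 5.4 both expect subjects to be followed off treatment. Rescue under 9.9.1 is extra U-500R in both arms, and a subject who abandons the pump can inject the same insulin, since "The U-500R insulin used in this study is commercially available in the US". Neither case needs to trigger the bullet. Much of this stands: it narrows the affected group and makes the bullet an option, not an order. It does not remove the problem, because the bullet's own wording describes study exit for a need that 8.3.2 does not address before the drug is taken.

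Two further replies also stand. The neighbouring bullet lets the investigator withdraw a subject for any reason, so rewording one bullet alone leaves another exit open. And a thin reference group is mainly a feature of the imputation design, for which SAP 5.9 already has a fallback. The 8.3.3 bullet can make that fallback more likely but does not create the weakness.

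A reader might infer more than the documents support:

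- **That exit is compulsory.** The lead-in is permissive and the bullet sits under investigator decision.
- **That both primary analyses lose data.** The MMRM excludes values after treatment discontinuation, so it would not use the lost value.
- **That noninferiority is biased in a known direction.** Nothing in the documents gives the number of such subjects, their outcomes or their split by arm.
- **That keeping such a subject breaches SAP deviation 42.** That entry concerns subjects who ought to have been discontinued, and a permissive clause creates no such duty.

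**Conclusion.** The point holds in limited form. Where a site follows the 8.3.3 bullet for a subject who would otherwise have attended Week 26, the FDA copy-reference analysis loses an observed HbA1c of the kind it was written to include. In the MDI arm it also loses a potential member of the SAP reference group. That is a stated rule working against the estimand of that analysis, not merely missing detail.

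The direct effect is about 0.003 to 0.006 HbA1c points on an arm mean per lost value, assuming an imputation error of 0.5 to 1.0. It is small unless many subjects are affected. The 0.063-point case is an extreme built on assumed inputs and is not an estimate. Severity is minor.

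**What to change.** Reword the 8.3.3 bullet along these lines: if a subject needs another agent that is effective for type 2 diabetes, stop study treatment under 8.3.2, ask the subject to stay in the study, and collect HbA1c and FPG at Visit 17 whatever the treatment at that time. Withdrawal of consent and the other study-exit reasons remain as they are.

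Limit the adjacent investigator-decision bullet so that starting another glucose-lowering agent is not by itself a reason for study exit. SAP deviation 42 needs no change.

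The cost is a short amendment or site letter and a few more off-treatment visits; the Visit 17 blood draw is already scheduled. The gain is confined to subjects still in follow-up. Amendment (a) was approved in December 2016, the month of the estimated last patient visit. On the planned dates few or none would benefit; actual dates are not given.

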8.3.4. Subjects Lost to Follow-Up

A subject will be considered lost to follow-up if he or she repeatedly fails to return for scheduled visits and is unable to be contacted by the study site. Site personnel are expected to make diligent attempts to contact subjects who fail to return for a scheduled visit or were otherwise unable to be followed up by the site.

Site personnel, or an independent third party, will attempt to collect the vital status of the subject within legal and ethical boundaries for all subjects randomized, including those who did not get study treatment. Public sources may be searched for vital status information. If vital status is determined, this will be documented and the subject will not be considered lost to follow up.

Lilly personnel will not be involved in any attempts to collect vital status information.

8.3.5. Discontinuation of Study Sites

Study site participation may be discontinued if Lilly, the investigator, or the ethical review board (ERB) of the study site judges it necessary for medical, safety, regulatory, or other reasons consistent with applicable laws, regulations, and GCP.

8.3.6. Discontinuation of the Study

The study will be discontinued if Lilly judges it necessary for medical, safety, regulatory, or other reasons consistent with applicable laws, regulations, and GCP.

9. Treatment

9.1. Treatments Administered

This study involves a comparison of U-500R administered by CSII with U-500R administered by MDI. [Table IBHD.9.1](#) shows the treatment regimens.

Table IBHD.9.1. Treatment Regimens

Regimen	Dose
U-500R CSII	Per titration algorithm (continuous infusion, injectable solution)
U-500R MDI	Per titration algorithm (TID, injectable solution)

Abbreviations: CSII = continuous subcutaneous insulin infusion; MDI = multiple daily injections; TID = three times daily.

The investigator or his/her designee is responsible for the following:

- explaining the correct use of the investigational agent(s) to the subject/site personnel,
- verifying that subject clearly understands instructions and is able to demonstrate understanding, maintaining accurate records of study treatment dispensing and collection, and returning all unused medication or devices to Lilly or its designee at the end of the study.

Note: In some cases, sites may destroy the material if, during the investigator site selection, the evaluator has verified and documented that the site has appropriate facilities and written procedures to dispose of clinical trial materials. In all other cases, the site has to return used or unused material to Lilly or designee.

Subjects will be instructed to contact the investigator as soon as possible if he or she has a complaint or problem with study treatment or drug delivery system so that the situation can be assessed.

9.2. Materials and Supplies

Subjects should continue taking their noninsulin pre-study AHA doses throughout the study, as applicable. Pre-study AHAs must be used as described in their respective product labeling.

Supplies and appropriate instructions for use will be provided for both treatment groups beginning at screening Visit 1 (Week -3). Study drug and additional supplies will be provided at Visits 4, 5, and as needed thereafter per the Study Schedule ([Attachment 1](#)).

Subjects will be assigned to treatment arm at randomization Visit 4 (Week 0). Appropriate pump training will be provided for the CSII group (Section [9.7.2](#)). The OmniPod U-500 system

supplies for infusion including PDM and Pod with fill syringe will be provided at Visit 6 (Week -2) and as needed thereafter per the study schedule.

U-500R will be provided in 20-mL vials (10,000 U) for use by CSII or MDI. Unopened U-500R vials or U-500R vials not in-use should be stored in a refrigerator (2° to 8°C [36° to 46°F]), but not in the freezer. Once opened, the U-500R vial can be kept unrefrigerated as long as it is kept as cool as possible (below 30°C [86°F]) and away from heat and light. In-use vials must be used within 40 days or be discarded, even if they still contain U-500R.

The respective labeling information will be provided with the insulin pump and supplies, the disposable syringes, and the study drug as applicable. In addition, a commercially available BG meter will be provided with necessary supplies and instructions at Visit 1 (Week -3). Clinical trial materials will be labeled according to the respective country's regulatory requirements.

Table IBHD.9.2. Study Devices

Regimen	Device	Device Details
U-500R CSII	OmniPod U-500 system ^a	CSII
U-500R MDI	BD U-100 insulin syringe and needle	0.5 mL syringe for ≤250-U dose; or 1.0 mL syringe for >250-U dose; 31 gauge; 6 mm length needle

Abbreviations: BD = Becton Dickinson; CSII = continuous subcutaneous insulin infusion; MDI = multiple daily injections; U = unit.

^a The OmniPod U-500 system is an investigational device.

9.3. Method of Assignment to Treatment

Subjects will continue on their pre-study insulin regimens until Visit 4 (Week 0). After re-confirmation of eligibility, subjects who meet specific criteria (Section 8) for enrollment will be randomized at Visit 4 (Week 0) to open-label treatment with U-500R administered by one of two treatment regimens: MDI or CSII. However, subjects randomized to CSII will not initiate U-500R administered by CSII until transition to U-500R is complete (Section 9.7). Assignment to treatment arms will be determined by a computer-generated random sequence using an IWRS.

9.4. Rationale for Selection of Doses in the Study

Protocol IBHD dosing transition to U-500R MDI and titration regimens for the CSII and MDI treatment groups are guided by initial insulin TDD (based on the highest TDD recorded in the 3 days before Visit 4), screening HbA1c (Visit 1), subsequent glucose monitoring, literature expert reviews (Lane 2006; Lane et al. 2009; Hirsch 2010, Lane et al. 2010; Segal et al. 2010; Reutrakul et al. 2012), efficacy and safety results from one Phase 4 clinical study (B5K-US-IBHC [Hood et al, 2015]), results from simulations performed using a systems physiology model of diabetes (Entelos PhysioLab® Modeler) based on data from previous pharmacodynamics/pharmacokinetics studies (de la Peña et al. 2011) of U-500R and U-100 Humulin regular insulin) and on expert protocol consultant advice.

Fasting and bolus for CSII and MDI therapy plasma-equivalent glucose target ranges are 80 to 140 mg/dL. Recommended administration of U-500R bolus doses, within approximately

30 minutes before meals by CSII or MDI dosing, is based on label advice and recent pharmacodynamics/pharmacokinetics study results in obese, healthy subjects that demonstrate both prandial and basal activity of U-500R (de la Peña et al. 2011). Administration of U-500R bolus doses 15 minutes before meals will be assessed in a subset of subjects participating in the continuous glucose monitoring (CGM) addendum to demonstrate glycemic impact. If the shorter bolus time period is found to be equally efficacious, there may be a potential benefit on adherence.

